Butler, Konstan, Morgan, & Wohl, 2003) and best practice sharing between centers (Schechter, Fink, Homa, & Goss, 2014). In 2017 all centers have now risen to near real-time reporting of lung function, exacerbation rates, weight and diabetes control trends for patients to encourage conversations and real behavior change around medical adherence.

The objective of this pilot study is to demonstrate the feasibility of integrating the personal health tracker data with the medical data stored in CFFPR to facilitate larger multicenter interventional studies to continue improving care in this deserving population.

Methods

Potential subjects will be identified during regular team meetings held by a dedicated care team for CF patients that includes members of the study staff. Patients who are identified as potential participants will be contacted by a trained member of the study team to discuss participation. The study team will work with patients to arrange for signing of an informed consent form at their next scheduled clinic appointment.

All subjects will be consented to participate in this observational study for a minimum 3 months to accommodate their clinic schedule. There will be a minimum of 2 clinical visits after enrollment (clinical visit 1 at set up and 2-5 months follow up) as well as any sick visits. This visit schedule was selected to coincide with current care schedules.

At the initial visit all consented subjects will be provided a Fitbit Inspire HR and shown the proper use and care of the tracker. The research coordinator will confirm the subject's ability to upload data from the device to their study Fitbit account (deidentified) under direct observation. The subjects will also receive instruction in how to document their activity and sleep in the diary app associated with their Fitbit. (The subjects will have access to instructional videos and help desk

through the Fitbit resource center as well). The research coordinator will monitor the study specific FitaBase for the duration of the study (once a week for 3 months) and contact the patient via their preferred method of contact with encouragement to consistently upload data if needed.

During the initial visit and any follow up clinic visits subjects will complete a general quality of life in CF survey-CF QOL and a sleep quality index-Pittsburgh Sleep Quality Index (PQSI) through Redcap to assist in a comprehensive integration of data.

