Clinical care visits and hospitalizations during the trial period of three months will be entered into the CFFPR national database (standard practice). Data of specific interest include: lung function (FEV1), BMI, and CF exacerbation rates. The exacerbation will be defined by the treating CF provider (generally this is reported as part of each visit (key features of a CF exacerbation include all the following but does not require any more than 3 of the following: Weight loss (>2 lbs.),

increased cough/increased sputum production, disturbed sleep due to coughing, increased fatigue/inability to do daily activities due to breathing problems/fatigue, fevers, fall in FEV1 by 5% or more)).

Any technical questions from the patient regarding the data collected by the fitness tracker will be answered by the research coordinator.

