2 HYPOTHESIS AND OBJECTIVES

This pilot, single center, correlational study will provide proof of concept for integrating existing medical data from CFFPR with long term monitoring of patterns in sleep and activity available through individual fitness trackers (i.e. Fitbit).

The data collected for each subject from the personal fitness monitors will be trended with daily, weekly and monthly averages over 3 months (activity level, time and intensity of exercise, sleep total time and quality

(percentage deep sleep). This information will be coupled with the CFFPR data health parameters as reported with every clinic visit and any hospitalizations for each subject.

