3.1.1 Primary Endpoint(s)

For Aim 1 and Aim 2 we will report descriptive statistics, such as mean, median and standard deviation, for the number of days of use, days of use over 20 hours and average hours of use per day (total hours of use/total days of use) in the study. Secondary Endpoint(s)

For Aim 3. We will conduct explorative data analysis to get preliminary information for designing a full-scale prospective study. First, we will report summary statistics, such as mean, median, standard deviation and quartile range, for continuous measurement and percentage for binary measurement, of heart rate, activity levels, sleep time and quality of sleep for every month and summary statistics for FEV1, BMI and CF exacerbation at enrollment and follow-up visit and differences between enrollment and follow-up visit. To identify what information of heart rate, activity levels, sleep time and quality of sleep is potentially associated with the differences between enrollment and follow-up visit in FEV1 and BMI and CF exacerbation, we will use Pearson correlations for FEV1 and BMI and comparing means or medians of the wearable metrics between the subgroups with and without CF exacerbation in 3 months. We will also consider mean or median values of the wearable metrics measured last 3-/2-/1-month prior to the follow-up to determine the extent to how latest metrics are associated with clinical outcomes.

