5.2 Study Withdrawal Procedures

5.2.1 Duration of Therapy: A patient may remain in the study up to 3-months.

5.2.2 Patient-Initiated Withdrawal: A patient may decide to withdraw from the study at any time.

5.2.3 Investigator-Initiated Withdrawal: The Investigator will withdraw a patient whenever continued participation is no longer in the patient's best interests. Reasons for withdrawing a patient include, but are not limited to, disease progression, the occurrence of an adverse event or a concurrent illness, a patient's request to end participation, a patient's noncompliance or simply significant uncertainty on the part of the Investigator that continued participation is prudent.

5.2.4 Withdrawal Documentation Procedure: The reason for study withdrawal and the date the patient was removed from the study must be documented in OnCore.

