6 TREATMENT PLAN

6.1 Standard of Care Procedures

6.2 Follow-Up Period

Patients will be followed for 90 days after enrollment or until death, whichever occurs first.

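### The protocol contradicts itself on how long participation and tracking last, when the follow-up visit falls and which time point the Aim 3 outcomes use, so the look-back windows are not defined

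*Combined protocol and SAP*

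**What the plan says.** Four things bear on the Aim 3 look-back analysis, and the current text gives more than one answer on each.

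- **Length of participation.** Section 5.2.1 sets a ceiling: "A patient may remain in the study up to 3-months". Section 6.2 agrees: "Patients will be followed for 90 days after enrollment or until death, whichever occurs first". The Methods part of section 1 sets a floor instead: "All subjects will be consented to participate in this observational study for a minimum 3 months to accommodate their clinic schedule". The Protocol Summary gives a follow-up duration of 3 to 5 months.
- **Length of tracking.** The Methods schedule upload checks "for the duration of the study (once a week for 3 months"), and section 2 has tracker data "trended with daily, weekly and monthly averages over 3 months". Eligibility (Protocol Summary and section 4.3) asks for a commitment of no less than 3 months. The Study Calendar marks device syncing at the follow-up visit, whenever that falls.
- **Follow-up visit.** The Methods describe "clinical visit 1 at set up and 2-5 months follow up", and the Protocol Summary and Study Calendar agree. The quality-control paragraph of the Methods calls the visit Month 3. Registry data are described for a shorter period: "Clinical care visits and hospitalizations during the trial period of three months will be entered into the CFFPR national database".
- **Aim 3 outcome time.** The Protocol Summary measures the FEV1 and BMI change from enrollment to 3 months. Section 3.1.1 measures it to the follow-up visit. Section 3.1.1 also treats CF exacerbation in two ways: as a difference to the follow-up visit, and as occurrence within 3 months.

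The look-back itself, in section 3.1.1, uses "mean or median values of the wearable metrics measured last 3-/2-/1-month prior to the follow-up".

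**The concern.** The look-back windows count backwards from the follow-up visit. They can be filled only if the tracker is still worn and uploaded in the weeks before that visit. A participant seen in month 4 or 5 is within the planned visit window but beyond the end of participation in sections 5.2.1 and 6.2, and beyond the period for which weekly upload checks are described. Two analysts who followed different sections could use different tracked days and different outcome times.

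There is a second effect. If visits anywhere from 2 to 5 months are analysed, FEV1 and BMI changes over quite different intervals enter one correlation, and the plan makes no allowance for elapsed time.

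What is at stake is the interpretability of an exploratory analysis. Its stated purpose is to inform the design of a full-scale study, so its exposure windows and outcome time should be fixed.

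**Working it through.** **1. The plan's own figures (section 9.2).** The 95% interval for a correlation, by Fisher z, is tanh(atanh(r) ± 1.96/√(n − 3)). With n = 21, 1.96/√18 = 0.462.

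- r = 0.1: tanh(0.562) − tanh(−0.362) = 0.510 + 0.347 = 0.856 (stated 0.856).
- r = 0.9: width 0.193 (stated 0.193).

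The half-width for a mean difference with SD 1 is t × √(1/n₁ + 1/n₂). This gives 0.940 for 10 and 10, and 0.969 for 7 and 14, both as stated. The precision figures are correct for 21 participants and are not in dispute.

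**2. Window coverage.** Inputs are the 2-to-5-month visit range (Protocol Summary, Study Calendar, Methods), the 90-day limit (section 6.2) and the three windows (section 3.1.1). I assume 30-day months. For a visit on day v, a window of w days and tracking that ends on day e:

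coverage = days common to [v − w, v] and [0, e], divided by w.

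| Visit day | Tracking to the visit (3-/2-/1-month) | Tracking stops at day 90, visit still analysed (3-/2-/1-month) |
|---|---|---|
| 60 | 67% / 100% / 100% | 67% / 100% / 100% |
| 75 | 83% / 100% / 100% | 83% / 100% / 100% |
| 90 | 100% / 100% / 100% | 100% / 100% / 100% |
| 105 | 100% / 100% / 100% | 83% / 75% / 50% |
| 120 | 100% / 100% / 100% | 67% / 50% / 0% |
| 135 | 100% / 100% / 100% | 50% / 25% / 0% |
| 150 | 100% / 100% / 100% | 33% / 0% / 0% |

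Examples: for v = 60 and w = 90, the window starts 30 days before enrollment, so coverage is 60/90 = 67% whenever tracking ends. For v = 120, w = 60 and e = 90, the window is days 60 to 120, of which 30 are tracked: 30/60 = 50%.

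**3. Interval for the FEV1 and BMI change.** If all visits in the planned range are analysed, the interval runs from about 60 to 150 days, and 150/60 = 2.5. If a Month 3 visit or a 3-month outcome governs, both the window gaps and the unequal intervals largely disappear.

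**4. Price of adjusting for elapsed days.** A partial correlation with one covariate has standard error 1/√(n − 4) on the z scale. With n = 21, 1.96/√17 = 0.475. The width goes from 0.856 to 0.878 at r = 0.1, and from 0.193 to 0.200 at r = 0.9.

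**The case against.** The best defence is that the protocol names its governing source. Section 3.2 says only to see the Study Calendar, and section 5.1.1 also points there. The calendar shows a 2-to-5-month visit with syncing marked at it, so tracking would run to the visit and the only defect would be a short 3-month window for early visits. The eligibility wording is a commitment that stopping at 3 months would satisfy. Month 3 is a parenthetical remark in a data-checking sentence, and the 3-month label in the Protocol Summary may be nominal. The flexible schedule was chosen deliberately to fit routine care, and the aim is exploratory.

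Much of this stands. The calendar does favour tracking to the visit. But pointing to the calendar does not cancel the limits in sections 5.2.1 and 6.2, and no passage states that wear and upload checks continue past month 3 for a participant seen late. Nor does the calendar settle whether the Aim 3 change runs to 3 months or to the visit.

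Two stronger readings are tempting. A reader might infer that the look-back windows will be empty for late visits. That requires the 90-day limit to apply to the tracker but not to the visit, and no passage says so: sections 5.2.1 and 6.2 do not mention the device. A reader might instead infer that outcomes after day 90 will be lost and the correlations will rest on fewer pairs. No passage says that such visits are to be discarded, and any count of them would need a visit distribution that the documents do not give.

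**Conclusion.** The contradiction is real and lies in current text: a cap of about 3 months on participation, against a follow-up visit planned at 2 to 5 months and a stated follow-up of 3 to 5 months. Two further inconsistencies concern the time point of the FEV1 and BMI change and the exacerbation period.

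The size depends on which sections are followed. On the reading that the calendar favours, the window defect is confined to the 3-month look-back for visits before day 90. That shortfall comes from the 2-month lower limit on the visit and would occur wherever tracking ended. The empty windows (1-month from day 120, 2-month at day 150) are conditional on tracking stopping at day 90 while later visits are analysed. The 2.5-fold spread in intervals applies only if all 2-to-5-month visits are used, and the bias from pooling them cannot be computed from the documents.

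These figures assume 30-day months. The planned number of participants, the precision statements in section 9.2, and Aims 1 and 2 are not shown to be affected. This is a matter of definition that deserves a short amendment; it does not undermine the study.

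**What to change.** Reconcile the Protocol Summary, the Methods in section 1, and sections 2, 3.1.1, 5.2.1 and 6.2 with the Study Calendar and section 3.2. The text should give one definition of the follow-up visit, one end of tracking and one Aim 3 outcome time. Then:

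- If the 2-to-5-month visit is kept, state that Fitbit data collection and upload checks continue to the later of month 3 and the follow-up visit.
- Define each look-back window by actual dates. Report days from enrollment to visit, and days of tracker data in each window.
- If 2-to-5-month visits are analysed, report the FEV1 and BMI correlations unadjusted and, as a sensitivity analysis, as partial correlations adjusted for days from enrollment to visit.
- State one exacerbation period and match the main wearable comparison to it. Keep the planned look-back comparison as a separate analysis, so that nothing in section 3.1.1 is dropped.

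The cost is an amendment with IRB approval (section 9.14). If late visits are kept, participants seen late have up to two more months of wear and upload checks; clinic visits do not change. The adjusted correlation uses one degree of freedom, with the small loss of precision shown in step 4 of the working.

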3.2 Study Timeline

See Study Calendar.

4 PATIENT SELECTION

4.1 Eligibility Criteria

Adults with Cystic Fibrosis

4.2 Inclusion Criteria

Age >18, Cystic Fibrosis

4.3 Exclusion Criteria

A potential subject who meets any of the following exclusion criteria is ineligible to participate in the study.

Those unable to commit to at least 3 months of participation with the fitness tracker and return for a routine follow up visit from time of enrollment at study CF center. Inability to speak and understand English. Those patients without dedicated access to a smartphone, tablet, or computer with internet for syncing device and completing patient diary. Those patients unwilling to sign an informed consent form.

5 STUDY ENTRY AND WITHDRAWAL; STUDY PROCEDURES

5.1 Study Entry Procedures

5.1.1 Required Screening

The study-specific assessments are detailed in this section and outlined in the Study Calendar.

When a CF patient 18 years of age or older is identified the study staff will review the inclusion/exclusion against the IRB approved criteria to ensure eligibility. If appropriate, they will pursue an informed consent discussion with the patient. All patients reviewed will be documented in a screening log and reason for exclusion for reporting purposes.

A signed ICF copy will be given to the subject and a copy will be filed in the medical record. The original will be kept on file with the study records.

All patients who are consented will be registered and randomized in OnCore®, the MCW Clinical Trial Management System. The system is password protected and meets HIPAA requirements.

Screening Assessments

- Confirmation of Eligibility Criteria listed in Section 4.2 and 4.3
- Signed written informed consent form by the patient

5.1.2 Study Procedures, Day 1

- all consented subjects will be provided a Fitbit Inspire HR and shown the proper use and care of the tracker. The research coordinator will confirm the subject's ability to upload data from the device to their

study Fitbit account (deidentified) under direct observation. The subjects will also receive instruction in how to document their activity and sleep in the diary app associated with their Fitbit. All subjects will have access to instructional videos and a help desk through the Fitbit resource center as well. The research coordinator will monitor the study database for the duration of the study and contact the patient via their preferred method of contact with encouragement to consistently upload data if needed. Collection of demographic information

5.1.3 Study Procedures During Visit 1 and Visit 2

- During Visit 1 and Visit 2, subjects will complete a general quality of life in CF survey (CFQ-R) and a sleep quality index-Pittsburgh Sleep Quality Index (PQSI) survey.

To provide up to date and accurate data from the device, subjects will need to sync their device at least every 5 days to store their activity information appropriately into the study database. In addition, the Fitbit app and website have additional programs including a diary where subjects can document their exercise, activity and even sleep habits. Whenever possible the subject will document their activity through this app to provide validation of the data collected by the sensors.

The study coordinator will confirm Fitbit uploads with the subject by comparison of the data entered in the patient activity/sleep diary entry to the data from the Fitbit during the phone call visits with the subject.

A database used for collecting the Fitbit data will only be given assigned subject codes to prevent sharing of identifiable subject information. To further secure patient privacy, all subjects will have a study email account set up to tie to the trackers during the study.

If the Fitbit stops working, the subject should contact the study coordinator to arrange for a replacement Fitbit. Fitbits that are lost will not be replaced.

5.2 Study Withdrawal Procedures

5.2.1 Duration of Therapy: A patient may remain in the study up to 3-months.

5.2.2 Patient-Initiated Withdrawal: A patient may decide to withdraw from the study at any time.

5.2.3 Investigator-Initiated Withdrawal: The Investigator will withdraw a patient whenever continued participation is no longer in the patient's best interests. Reasons for withdrawing a patient include, but are not limited to, disease progression, the occurrence of an adverse event or a concurrent illness, a patient's request to end participation, a patient's noncompliance or simply significant uncertainty on the part of the Investigator that continued participation is prudent.

5.2.4 Withdrawal Documentation Procedure: The reason for study withdrawal and the date the patient was removed from the study must be documented in OnCore.

6 TREATMENT PLAN

6.1 Standard of Care Procedures

6.2 Follow-Up Period

Patients will be followed for 90 days after enrollment or until death, whichever occurs first.

7 ADVERSE EVENTS: DEFINITIONS AND REPORTING REQUIREMENTS

7.1 Definitions

7.1.1 Adverse Event (AE) and Serious Adverse Events (SAE)

Patients enrolling in this trial are not expected to have any adverse events related to the study. Should an event occur the investigator and his or her team will follow the Medical College of Wisconsin policies related to adverse event reporting. This information may be found on the [Human Research Protection Program website](#).

Serious AE (SAE) means any untoward medical occurrence related to study specific procedures/interventions:

- **Death.** Results in death.
- **Life threatening.** Is life threatening (refers to an AE in which the patient was at risk of death at the time of the event. It does not refer to an event which hypothetically might have caused death if it were more severe).
- **Hospitalization.** Requires inpatient hospitalization or prolongation of an existing hospitalization (see clarification in the paragraph below on planned hospitalizations).
- **Disability/incapacity.** Results in persistent or significant disability or incapacity. (Disability is defined as a substantial disruption of a person's ability to conduct normal life functions).
- **Medically important event.** This refers to an AE that may not result in death, be immediately life threatening, or require hospitalization, but may be considered serious when, based on appropriate medical judgment, may jeopardize the patient, require medical or surgical intervention to prevent 1 of the outcomes listed above, or involves suspected transmission via a medicinal product of an infectious agent. Examples of such medical events include allergic bronchospasm requiring intensive treatment in an emergency room or at home, blood dyscrasias or convulsions that do not result in inpatient hospitalization, or the development of drug dependency or drug abuse; any organism, virus, or infectious particle (e.g., prion protein transmitting Transmissible Spongiform Encephalopathy), pathogenic or nonpathogenic, is considered an infectious agent.

Clarification should be made between a serious AE (SAE) and an AE that is considered severe in intensity (Grade 3 or 4), because the terms serious and severe are NOT synonymous. The general term severe is often used to describe the intensity (severity) of a specific event; the event itself, however, may be of relatively minor medical significance (such as a Grade 3 headache). This is NOT the same as serious, which is based on patient/event outcome or action criteria described above and is usually associated with events that pose a threat to a patient's life or ability to function. A severe AE (Grade 3 or 4) does not necessarily need to be considered serious. For example, a white blood cell counts of 1000/mm³ to less than 2000 is considered Grade 3 (severe) but may not be considered serious. Seriousness (not intensity) serves as a guide for defining regulatory reporting obligations.

7.1.2 Unanticipated Problem Involving Risk to Subject or Other (UPIRSO)

The investigator and his or her team will follow the Medical College of Wisconsin policies related to unanticipated problems involving risks to subjects or others. This information may be found on the [Human Research Protection Program website](#).

7.1.3 AE Attribution and Grading

Adverse Event Grading

Grade	Description
0	No AE (or within normal limits).
1	Mild; asymptomatic or mild symptoms; clinical or diagnostic observations only; intervention not indicated.
2	Moderate; minimal, local or noninvasive intervention (e.g., packing cautery) indicated; limiting age-appropriate instrumental activities of daily living (ADL).
3	Severe or medically significant but not immediately life-threatening; hospitalization or prolongation of hospitalization indicated; disabling; limiting self-care ADL.
4	Life-threatening consequences; urgent intervention indicated.
5	Death related to AE

Adverse Event Attribution

Attribution is an assessment of the relationship between the AE and the medical intervention.

Relationship	Attribution	Description
Unrelated to investigational agent/intervention	Unrelated	The AE is clearly NOT related to the intervention
	Unlikely	The AE is doubtfully related to the intervention
Related to investigational agent/intervention	Possible	The AE may be related to the intervention
	Probable	The AE is likely related to the intervention
	Definite	The AE is clearly related to the intervention

Relationship Assessment: In-Depth Definitions

For all collected AEs, the clinician who examines and evaluates the subject will determine the adverse event's causality based on temporal relationship and his/her clinical judgment. The degree of certainty about causality will be graded using the categories below:

Definitely Related: There is clear evidence to suggest a causal relationship, and other possible contributing factors can be ruled out. The clinical event, including an abnormal laboratory test result, occurs in a plausible time relationship to drug administration and cannot be explained by concurrent disease or other drugs or chemicals. The response to withdrawal of the drug (dechallenge) should be clinically plausible. The event must be pharmacologically or phenomenologically definitive, with use of a satisfactory rechallenge procedure if necessary.

Probably Related: There is evidence to suggest a causal relationship, and the influence of other factors is unlikely. The clinical event, including an abnormal laboratory test result, occurs within a reasonable time sequence to administration of the drug, is unlikely to be attributed to concurrent disease or other drugs or chemicals, and follows a clinically reasonable response on withdrawal (dechallenge). Rechallenge information is not required to fulfill this definition.

Possibly Related: There is some evidence to suggest a causal relationship (e.g., the event occurred within a reasonable time after administration of the trial medication). However, the influence of other factors may have contributed to the event (e.g., the subject's clinical condition, other concomitant events). Although an adverse drug event may rate only as "possibly related" soon after discovery, it can be flagged as requiring more information and later be upgraded to "probably related" or "definitely related", as appropriate.

Unlikely: A clinical event, including an abnormal laboratory test result, whose temporal relationship to drug administration makes a causal relationship improbable (e.g., the event did not occur within a reasonable time after administration of the trial medication) and in which other drugs or chemicals or underlying disease provides plausible explanations (e.g., the subject's clinical condition, other concomitant treatments).

Unrelated: The AE is completely independent of study drug administration, and/or evidence exists that the event is definitely related to another etiology. There must be an alternative, definitive etiology documented by the clinician.

